6.1 Primary objective

- To evaluate the non-inferiority of immunogenicity in participants aged 6-35 months after 2 doses of 0.5mL-dose QIV compared with two TIVs (including BV or BY) for the shared strains, in terms of seroconversion rate (SCR) and Geometric mean titer (GMT) for HI antibody;
- To evaluate the non-inferiority of immunogenicity in participants aged 6-35 months after 2 doses of 0.25mL-dose QIV compared with two TIVs (including BV or BY) for the shared strains, in terms of SCR and GMT for HI antibody;
- To evaluate the absolute criteria of HI antibody SCR and seroprotection rate (SPR) for each strain in participants aged 6-35 months after two doses of 0.25mL-dose or 0.5mL-dose QIVs.

6.2 Secondary objective

- To evaluate the non-inferiority of immunogenicity in participants aged 6-35 months after 2 doses of 0.5mL-dose QIV compared with 0.25mL-dose QIV for each strain, in terms of seroconversion rate and GMT of HI antibody;
- To evaluate the superiority of immunogenicity in participants aged 6-35 months after 2 doses of 0.25mL-dose or 0.5mL-dose QIVs compared with two TIVs (including BV or BY) for the unique strain, in terms of seroconversion rate and GMT of HI antibody;
- To evaluate the immunogenicity in participants aged 6-35 months after vaccination of 2 doses of 0.25mL-dose or 0.5mL-dose QIVs;
- To evaluate the safety of 0.25mL-dose or 0.5mL-dose QIVs in participants aged 6-35 months.

7. Study design

7.1 Design

7.1.1 Overall study design

A multi-centered, randomized, blinded (double-blinded), and controlled trial design.

7.1.2 Sample size calculation

This trial requires the test group: ① the non-inferiority comparison with the control groups is established and the next statistical test is carried out; ② when the absolute criteria of SCR and SPR are achieved, the trial can be considered as successful and a positive conclusion can be drawn for the test group. In this trial, when evaluating between the test group 1 (0.25-mL QIV) and test group 2 (0.5mL-QIV), the strategy of sequential test is adopted. First, test group 2 is evaluated. If the positive conclusion of test group 2 is established, test group 1 is further evaluated. Therefore, class I error correction is no longer carried out. The sample size of phase III clinical trials is estimated first by non-inferiority design, namely the QIV group is non-inferior to the TIV group. The primary endpoints of this study include two indicators: SCR and GMT. Only when the SCR and GMT of four serotypes in test group are non-inferior to the control vaccine, the investigational vaccine is considered to be non-inferior to the control vaccine. The total power is 80%, the type II

error is 0.2. Based on the different sample size requirements of the two indicators, the type II error is allocated, with 0.16 for seroconversion rate comparison and 0.04 for GMT comparison.

(1) Calculation of sample size with the SCR as the indicator:

According to the results of the previous Anflu phase IV clinical trial and other literature, the SCR of the types contained in the vaccine 28 days after vaccination is over 65%, which is used as the reference proportion to estimate the sample size. The test level is taken as one-sided $\alpha=0.025$, the power of non-inferiority comparison for the seroconversion rate of a serotype is taken as $1-\beta_1/4=1-0.16/4=96\%$, and the non-inferiority threshold Δ is taken as -10%. When comparing the non-inferiority of BY or BV strain, NT:NC=2:1, and PASS software is used to calculate the sample size, the test group needs 914 samples and the control group needs 457 samples. When the non-inferiority test of H1N1 or H3N2 strain is carried out, two control groups are pooled. The sample size ratio of the test group and the pooled control group is 1:1, and the test group and the pooled control group need 625 participants.

(2) Calculation of sample size with the GMT as the indicator:

Using the antibody GMT 28 days after vaccination as the outcome measure, the non-inferiority margin is $\geq 2/3$ of the 95%CI lower limit of GMT ratio between the test group and the control group, and the non-inferiority margin after logarithmic conversion is $\Delta=-0.176$. The test level is taken as one-sided $\alpha=0.025$, and the power of a certain serotype GMT for non-inferiority comparison is taken as $1-\beta_2/4=1-0.04/4=99\%$, and the standard deviation after logarithmic transformation is taken as $\sigma=0.7$ with reference to the previous research results. When comparing the non-inferiority of BY or BV, NT:NC=2:1, and PASS software is used to calculate the sample size, the test group needs 874 samples and the control group needs 437 samples. When the non-inferiority test of H1N1 or H3N2 type is carried out, two control groups are pooled. The sample size ratio of the test group and the pooled control group is 1:1, and the test group and the pooled control group need 582 participants each.

When the SCR and GMT of the test group reach the hypothesis of non-inferiority, the absolute criteria of the SCR and seroprotection rate (SPR) of the test group are further hypothesized for test. The trial requires that the SCR and SPR of the four strains of immune antibodies reach the absolute criteria, and the total power of the trial is 80%, so the power of each test is $1-(0.2/8)=0.975$.

(3) Calculation of sample size with the absolute criteria of SCR:

Assuming that the SCR after vaccination is 65%, the test level is one-sided $\alpha=0.025$, the lower limit of the confidence interval of the seroconversion rate should be greater than 30%, and the power of each test is 97.5%. The sample size is calculated by PASS software, and the test group needs 28 samples.

(4) Calculation of sample size with the absolute criteria of SPR:

Assuming that the seroconversion rate after vaccination is 75%, the test level is one-sided $\alpha=0.025$, the lower limit of the confidence interval of the SPR should be greater than 60%, and the power of each test is 97.5%. The sample size is calculated by PASS software, and the test group needs 146 samples.

In consideration of the above the maximum sample size and the dropout rate of about 17%, the sample size of each test group is 1,100, and the sample size of each control group is 550, with a total sample size of 3,300.

7.2 Study endpoint

Co-primary endpoint and evaluation criteria:

(1) The HI antibody GMTs and SCRs for each of the four strains in QIV groups were inferior to those of control groups at 28 days after vaccination in total populations. The non-inferiority criteria are as follows:

- **GMTs:** Non-inferiority of GMTs was demonstrated if the lower limit of the two-sided 95% confidence interval (CI) for adjusted GMT ratio (test group/control group) $\geq 2/3$ for each of the four strains.
- **SCRs:** The percentages of participants with either a pre-vaccination titer $<1:10$ and a post-vaccination titer $\geq 1:40$, or a pre-vaccination titer ≥ 10 and a ≥ 4 -fold increase in post-vaccination titer at 28 days after vaccination. Non-inferiority for SCR was demonstrated if the lower limit of the two-sided 95% CI for SCR difference (test group-control group) was $\geq -10\%$ for each of the 4 strains.

(2) The SCRs and SPRs should meet the absolute criteria in total populations.

- Absolute criteria of SCR and SPR: the lower limit of the two-sided 95%CI for SCR was $\geq 30\%$; the lower limit of the two-sided 95%CI for SPR was $\geq 60\%$.

Second endpoint and evaluation criteria:

➤ **Immunogenicity endpoint**

(1) The HI antibody GMTs and SCRs for the unique B strain in QIV groups were superior to those of control groups at 28 days after vaccination in total populations. The criteria for superiority were as follows:

- The lower limit of the two-sided 95%CI for adjusted GMT ratio (test group/control group) ≥ 1.5 ;
- The lower limit of the two-side 95% CI for SCR difference (test group-control group) was $\geq 10\%$.

(2) The HI antibody GMTs and SCRs for each of the four strains in 0.5mL-dose QIV group were inferior to those of 0.25-mL-dose QIV at 28 days after vaccination in total populations. The non-inferiority criteria were consistent with the co-primary endpoints.

(3) The HI antibody GMIs of each strain at 28 days after second vaccination in total population;

(4) The HI antibody SCRs, SPRs, GMTs and geometric mean fold increasing (GMFIs) of 0.5mL-dose QIV and 0.25mL-dose QIV in susceptible population (HI antibody titers $<1:10$). The non-inferiority, superiority and absolute criteria refer to the total population.

➤ **Safety endpoint**

- (1) Incidence of adverse reactions in 0-28 days after each dose of QIVs;
- (2) Incidence of adverse reactions in 0-7 days after each dose of QIVs;
- (3) Incidence of SAE from the beginning of the first dose to 6 months after second dose;
- (4) Incidence of AESI from the beginning of first dose to 6 months after second dose.

7.3 Estimand

7.3.1 Primary Estimand

Table 3 Primary Estimand

	Primary Estimand
Population	The target population involves all participants aged 6 to 35 months who have completed two doses of vaccination.
Variable	
(1) Whether the H1N1 and H3N2 HI antibodies are seroconverted in the test group (0.5mL or 0.25mL) and the pooled TIV group 28 days after the second dose.
 
(2) Whether the BV HI antibody is seroconverted in the test group (0.5mL or 0.25mL) and the TIV-BV groups 28 days after the second dose.
 
(3) Whether the BY HI antibody is seroconverted in the test group (0.5mL or 0.25mL) and the TIV-BY group 28 days after the second dose.
 
(4) H1N1 and H3N2 HI antibody titers of the test group (0.5mL or 0.25mL) and the pooled TIV group 28 days after the second dose.
 
(5) BV HI antibody titers of the test group (0.5mL or 0.25mL) and the TIV-BV groups 28 days after the second dose.
 
(6) BY HI antibody titers of the test group (0.5mL or 0.25mL) and the TIV-BY group 28 days after the second dose.
 
(7) Whether the H1N1, H3N2, BV, and BY HI antibody titer reach the protective antibody level in the test group (0.5mL or 0.25mL) 28 days after the second dose.

Treatments	Subjects received two doses of the test vaccine or the control vaccine according to the 0,28-day schedule.
Intercurrent Events and Treatment Strategies	The definition is shown in Table 4.
Population-level Summary	
(1) Difference between the SCRs of H1N1 and H3N2 HI antibodies of the test group (0.5mL or 0.25mL) and the pooled TIV group 28 days after the second dose.
 
(2) Difference between the SCRs of BV serum HI antibodies of the test group (0.5mL or 0.25mL) and the TIV-BV group 28 days after the second dose.
 
(3) Difference between the SCRs of BY HI antibodies of the test group (0.5mL or 0.25mL) and the TIV-BY group 28 days after the second dose vaccination.
 
(4) GMT ratios of H1N1 and H3N2 HI antibodies of the test group (0.5mL or 0.25mL) and the pooled TIV group 28 days after the second dose
 
(5) GMT ratios of BV serum HI antibodies of the test group (0.5mL or 0.25mL) and the trivalent control group (including BV) after 28 days of full-course vaccination.
 
(6) GMT ratios of BY serum HI antibodies of the test group (0.5mL or 0.25mL) and the trivalent control group (including BY) after 28 days of full-course vaccination.
 
(7) Seroprotection rates (SPRs) of H1N1, H3N2, BV, and BY HI antibody in the test group (0.5mL or 0.25mL) after 28 days after the second dose.

Table 4 Intercurrent Events and Treatment Strategies of Primary Estimand

7.3.2 Secondary Estimand 1

Table 5 Secondary Estimand 1

Secondary Estimand 1	
Population	The target population involves all participants aged 6 to 35 months who have completed two doses of vaccination.
Variable	(1) Whether the H1N1, H3N2, BV, and BY HI antibodies are seroconverted in both the test group 2 (0.5mL) and the test group 1 (0.25mL) 28 days after the second dose. (2) H1N1, H3N2, BV, and BY serum HI antibody titers of the test group 2 (0.5mL) and the test group 1 (0.25mL) 28 days after the second dose.
Treatments	As the same as the primary estimand
Intercurrent Events and Treatment Strategies	As the same as the primary estimand
Population-level Summary	(1) Difference between the SCR of H1N1, H3N2, BV, and BY serum HI antibodies of the test group (0.5mL) and the test group (0.25mL) 28 days after the second dose. (2) GMT ratios of H1N1, H3N2, BV, and BY serum HI antibodies between the test group (0.5mL) and the test group (0.25mL) 28 days after the second dose.

7.3.3 Secondary Estimand 2

Table 6 Secondary Estimand 2

	Secondary Estimand 2
Population	The target population involves all participants aged 6 to 35 months who have completed two doses of vaccination.
Variable	(1) Whether the BV HI antibody is seroconverted in the test group (0.5mL or 0.25mL) and the TIV-BY group 28 days after the second dose. (2) Whether the BY HI antibody is seroconverted in the test group (0.5mL or 0.25mL) and

Secondary Estimand 2	
	the TIV-BV group 28 days after the second dose. (3) BV HI antibody titers of the test group (0.5mL or 0.25mL) and the TIV-BY group 28 days after the second dose. (4) BY HI antibody titers of the test group (0.5mL or 0.25mL) and the TIV-BV group 28 days after the second dose.
Treatments	As the same as the primary estimand
Intercurrent Events and Treatment Strategies	As the same as the primary estimand
Population-level Summary	(1) Difference between the SCRs of BV HI antibody of the test group (0.5mL or 0.25mL) and TIV-BY group 28 days after the second dose. (2) Difference between the SCRs of BY serum HI antibody of the test group (0.5mL or 0.25mL) and TIV-BV 28 days after the second dose. (3) GMT ratios of BV HI antibodies of the test group (0.5mL or 0.25mL) and the TIV-BY group 28 days after the second dose. (4) GMT ratios of BY HI antibodies of the test group (0.5mL or 0.25mL) and the TIV-BV group 28 days after the second dose.

7.3.4 Secondary Estimand 3

Table 7 Secondary Estimand 3

Secondary Estimand 3	
Population	The target population involves the subjects (susceptible population) with the HI antibody titer <1:10 before immunization, aged 6 to 35 months, who have completed the full-course vaccination of two doses.
Variable	As the same as the primary estimand
Treatments	As the same as the primary estimand
Intercurrent Events and Treatment Strategies	As the same as the primary estimand
Population-level Summary	As the same as the primary estimand

7.4 Study plan

This trial is a multi-center, randomized, double-blinded, and positive-controlled design. The control vaccine is Anflu®, two 0.25mL-dose trivalent influenza virus split vaccines (TIVs, containing a B Victoria lineage or B Yamagata lineage) marketed by Sinovac. This trial will be conducted on children aged 6 to 35 months with the informed consent of their guardians. A total of 3,300 participants are planned to be recruited and randomly assigned to 4 groups in a ratio of 2:2:1:1, namely the 0.25mL-dose QIV group, 0.5ml-dose QIV group, TIV-BV group, and TIV-BY group. All participants receive 2 doses of the test vaccine or control vaccine according to the 0, 28-day immunization schedule.

All participants are observed for immediate reactions for 30 minutes after each dose, solicited systemic and local adverse events within 0-7 days, and unsolicited adverse events within 0-28 days after each dose. Additionally, monitoring of serious adverse events (SAEs) and adverse events of special interest (AESIs) is conducted from the first dose administration to 6 months after the second vaccination to evaluate the safety. Venous blood samples are collected from all participants before immunization and 28 days after the second immunization for hemagglutination inhibition (HI) antibody detection to assess the immunogenicity of the vaccine.

Table 8 Study design

Group	Vaccines	Sample size	Immunization schedule (days)	Blood sample collection (days)
Test group 1	Influenza Vaccine (Split Virion), Inactivated, Quadrivalent (0.25mL)	1100	0,28	0,56
Test group 2	Influenza Vaccine (Split Virion), Inactivated, Quadrivalent (0.5mL)	1100	0,28	0,56
	Influenza Vaccine (Split Virion),			0,56
Control group 1	Inactivated, Anflu (0.25mL, including BV)	550	0,28	
Control group 2	Inactivated, Anflu (0.25mL, including BY)	550	0,28	
Total		3300		

7.5 Randomization and blinding

7.5.1 Randomization

This clinical trial is a randomized, blinded, positive-controlled design. Then, random blind code will be generated by a third-party randomization statistician independent of the project using the SAS statistical software (version 9.4) according to the preset block lengths, and the range of random numbers is specified in the "Randomization protocol". Vaccines are randomized and blinded according to random numbers. The blind code of investigational vaccines is the "List of Correspondence Between Investigational Vaccine Codes and Vaccine Groups", will be stored by the randomization statistician.

At the same time, the randomization statistician uses SAS statistical software to generate the backup vaccine blind code. When the investigational vaccine is damaged, the vaccinator should report to the on-site technical head and the Principal Investigator to start the spare vaccine program. The numbers of backup vaccines are specified in the "Randomization Scheme". All investigational vaccines need to be re-labeled with blind labels, and the label format is detailed in "6.7 Vaccine Packaging". After enrollment, each subject will receive the blinded vaccine corresponding to their study number.

7.5.2 Blinding

This clinical trial adopts a double-blind design. Randomization statisticians and other blinding staff who did not participate in the trial performed vaccine blinding, that is, pasting the printed label on the designated position of each vaccine according to the blind code. The randomization statistician

supervises the blinding of vaccines, and guides the blinding operators to label according to the blind code. After completion of blinding, the blind code should be sealed by the randomization statistician. The entire process of blinding must be recorded. The blinding personnel must not be involved in other relevant work in this clinical trial or reveal the blind code to anyone who is involved in this clinical trial.

Considering 0.25mL and 0.5mL investigational vaccines were used for this clinical trial, the following measures were taken to maintain the blind status of the study process:

- (1) Investigators engaged in vaccination and vaccine administrators must sign confidentiality agreements, and cannot participate in other clinical work involving research information of participants;
- (2) After verifying that the information of the participants is correct, the vaccine administrator should take out the vaccine with the corresponding number and submit it to the vaccinators in this group. The vaccinators must check the information of the participants again and carry out vaccination after confirmation;
- (3) Each participant must be vaccinated individually, meaning that there are only the vaccination personnel, the subject, and his/her accompanying person in the vaccination room during each vaccination.

7.5.3 Emergency Unblinding

Based on the safety of participants and other special reasons, the treatment group information of individual or some participants can be obtained in emergency situations in accordance with pre-established standard operating procedures (SOPs). For both expected and unexpected serious adverse events, emergency unblinding shall only be conducted when researchers must know the group information due to an emergency involving the subject (e.g., requiring rescue). If knowledge of the group information is not necessary for handling the emergency, emergency unblinding is not required.

Once emergency unblinding occurs, the time, reason, and executor of the emergency unblinding must be recorded promptly. Meanwhile, the monitor shall be notified as soon as possible, and a safety event report shall be submitted to the Ethics Committee. After the trial is completed, the number, reasons, scope, and timing of emergency unblinding shall be described and analyzed, serving as a reference for the evaluation of immunogenicity and safety.

7.5.4 SUSAR Unblinding

In the event of a suspected unexpected serious adverse reaction (SUSAR), the sponsor needs to unblind the individual case report to facilitate judging the correlation between the serious adverse event and the trial vaccine and determining whether rapid reporting is required.

This clinical trial adopts a blinded design. When a situation requiring SUSAR unblinding occurs, the non-blinded pharmacovigilance personnel shall apply to the randomization statistician via email for the blind code information of the corresponding subject. After unblinding, if the vaccine involved is the trial vaccine, it shall be submitted in accordance with the rapid reporting procedures and requirements; the reporting method is specified in the submission process from the sponsor to the regulatory authorities in "9.7.6 Reporting of Serious Adverse Events". This unblinding process

shall be conducted independently, and the SUSAR unblinding of individual case reports will not affect the implementation of the clinical trial or the analysis of the final results.

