9.7.4 Correlation of adverse events and vaccines

The investigators should do their best to explain AE and to evaluate its possible causality, that is, the causality between the investigated vaccine and the alternative causes (such as history of underlying disease and the combined treatment), which applies to all AE, both serious and non-serious.

Causality assessments will be determined by the extent to which the events can be reasonably explained in one or more of the following:

A reasonable temporal relationship between the administration of the trial vaccine and the occurrence of adverse events

Reactions of similar nature have previously been observed in this type of vaccine;

Same events have been reported in the literature with regard to the similar types of vaccine;

The occurrence of the event coincided with the vaccination of the administration of the investigational vaccine; and occur again after the re-administration of the vaccine.

The occurrence of the event can be explained by the effects of concomitant medications (vaccines) or the impact of other treatments

AE Causality should be assessed, by the investigator, to ensure whether there is a reasonable possibility that the AE is caused by the administration of the vaccine, based on the following:

General principles for the correlation judgment:

- ✓ **Certainly related:** there is evidence of vaccination with the experimental vaccines; the occurrence of adverse events and the time sequence of the test vaccine administration are reasonable; adverse events are more likely to be explained by the test vaccines than by other causes; positive results after repeated administration of the test vaccine; adverse events are consistent with the prior knowledge of this type or these types of the vaccine.
- ✓ **Probably related:** there is evidence of vaccination with the experimental vaccines; the occurrence of adverse events and the time sequence of the test vaccine administration are reasonable; adverse events are more likely to be explained by the test vaccines than by other causes.
- ✓ **Possibly related:** there is evidence of vaccination with the experimental vaccines; the occurrence of adverse events and the time sequence of the test vaccine administration are reasonable; the occurrence of the adverse events cannot be ruled out as a result of the test vaccine and possibly may be caused by other reasons.

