9.7.6 Report serious adverse events

(1) Reporting Procedures for Investigators

The study institutions shall establish an emergency response plan for SAE handling. Upon learning of an SAE, regardless of whether it is related to the trial vaccine, the investigator must immediately (within 24 hours as required) fill out the Serious Adverse Event Report Form, send the initial report to the sponsor (via the dedicated pharmacovigilance email for clinical trials: [REDACTED]), and copy the report administrator. In case of emergency, the 24-hour emergency contact can also be reached [REDACTED]. Subsequent supplementary information/reports shall be submitted as soon as possible until the event is resolved.

When filling out the Serious Adverse Event Report Form, the investigator shall report the entire situation in writing, including but not limited to the name and relevant description of the adverse event, the occurrence time and type of the SAE, duration, severity, causal relationship with

vaccination, outcome, measures taken (symptomatic treatment), and other relevant clinical and laboratory data.

In case of a death event, the investigator shall report to the sponsor and the EC, and provide the autopsy report and final medical report.

Meanwhile, the clinical trial responsible institution/investigator shall promptly forward the sponsor's latest safety information reports on the clinical trial to the EC.

The EC shall receive SAE reports and other safety information reports, keep abreast of the occurrence and handling of SAEs throughout the clinical trial, and conduct follow-up reviews on the handling and reporting of SAEs during the trial.

(2) Reporting Procedures for the Sponsor

The day on which the sponsor first becomes aware of a valid report is designated as Day 0. After receiving the SAE reported by the investigator, the sponsor's pharmacovigilance personnel shall immediately review the completeness and accuracy of the original data. If necessary, they shall send inquiries to the investigator. At the same time, the sponsor shall analyze and evaluate the report, including the severity, relevance to the trial vaccine, and whether it is an unexpected event.

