6.9.2 Serious Adverse Event

This trial mainly conducted statistical analysis on SAEs that occurred after the first dose of vaccination, including those that occurred within 6 months from the first dose of vaccination to the full course of vaccination.

The number of events, number of subjects, and incidence rates of the following types of serious adverse events will be calculated, respectively, by total and for each group. Fisher's exact test will be used to test the differences between groups.

The number, number of cases and incidence of the following SAEs will be calculated by each group and the total. Fisher's exact test will be used to statistically test the differences between groups:

- All SAEs.
- SAEs related to the investigational vaccine.
- SAEs unrelated to the investigational vaccine.

List all SAEs.

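### Protocol 7.5.4 opens the code to help the sponsor judge whether a suspected SUSAR is related, and neither document fixes the blinded causality call as the one analysed

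*Protocol*

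**What the plan says.** **Unblinding.** For a SUSAR, Protocol 7.5.4 states that "the sponsor needs to unblind the individual case report to facilitate judging the correlation between the serious adverse event and the trial vaccine"; a second purpose is to decide whether rapid reporting is needed. The route is that "the non-blinded pharmacovigilance personnel shall apply to the randomization statistician via email for the blind code information of the corresponding subject". If the child received the trial vaccine, the case is then sent for rapid reporting. The section adds that "the SUSAR unblinding of individual case reports will not affect the implementation of the clinical trial or the analysis of the final results".

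**Causality.** Protocol 9.7.4 names the assessor: "AE Causality should be assessed, by the investigator, to ensure whether there is a reasonable possibility that the AE is caused". Under 9.7.6, on learning of an SAE, "the investigator must immediately (within 24 hours as required) fill out the Serious Adverse Event Report Form", and the form covers "the occurrence time and type of the SAE, duration, severity, causal relationship with" vaccination. After receiving it, "the sponsor shall analyze and evaluate the report, including the severity, relevance to the trial vaccine, and whether it is an unexpected event". If the two parties disagree and either cannot rule out a relationship, the sponsor must still report.

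**Use of the result.** SAP 6.9.2 counts "SAEs related to the investigational vaccine" by group and applies Fisher's exact test. SAP 6.9.3 does the same for related AESIs. SAP 6.1.2 says which causality categories count as related, but not who assigns them. Protocol 7.8 makes a fatal or life-threatening SUSAR one of the suspension criteria.

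**The concern.** A causality judgment made with knowledge of the vaccine is open to bias. A sponsor that knows whether the child had the new QIV or its own marketed type of TIV may read the same facts differently. The usual protection is order: relatedness and expectedness are settled first, and the code is opened afterwards only to handle the report. Section 7.5.4 gives help with the relatedness judgment as a reason for opening the code, which reverses that order.

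Two things are at stake. One is the integrity of the sponsor's causality and SUSAR classification, on which expedited reporting and one limb of the suspension rule rest. The other is whether the related-SAE and related-AESI tables can be shown to rest on blinded calls.

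**Working it through.** The plan gives no figure on this point, so the check is to set the sections side by side.

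1. **7.5.4 against the SUSAR definition in Protocol 9.7.2.** The definition covers a reaction that is already suspected and unexpected. By the time 7.5.4 applies, suspicion and unexpectedness should both have been established. Opening the code to help judge relatedness is therefore circular.

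2. **7.5.4 against 9.7.6.** In 9.7.6 the sponsor judges relatedness and expectedness on receipt of the SAE report, with no mention of the code. In 7.5.4 the code helps with the same judgment. A reader cannot tell whether the sponsor's causality call is blinded.

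3. **Does the unblinded call reach the analysis?** The investigator assesses causality (9.7.4) and records it on a form due within 24 hours (9.7.6). Under 7.5.4 the code goes to unblinded pharmacovigilance staff for one child, not to the investigator. Protocol 7.5.5 keeps observation, result-judgment and data-verification staff blinded until final lock. No section says that the sponsor's opinion replaces the investigator's. The link is not stated.

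4. **Is it excluded?** It is not. The form in 9.7.6 is an initial report: supplementary reports follow until the event resolves, and the sponsor may query the investigator meanwhile. No section locks the first call. SAP 6.1.2, 6.9.2 and 6.9.3 name neither assessor nor version. The labels do not settle the source, because SAP 6.1.2 uses a definite category and two unrelated categories that are worded differently from those in Protocol 9.7.4.

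5. **Suspension (7.8).** The section does not say whether SUSAR status is set before or after the code is opened. A separate limb covers Grade 4 vaccine-related events, and the investigators' view prevails in a disagreement.

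6. **Size.** The planned arms are 1,100 per QIV group and 550 per TIV group.
   - One event reclassified in a QIV arm: 1/1,100 = 0.09 percentage points.
   - One event reclassified in a TIV arm: 1/550 = 0.18 percentage points.
   - Effect on a test, if the only related SAE is one in a TIV arm compared with none in a QIV arm: Fisher's p = 550/(550 + 1,100) = 0.33. Removing that event changes no inference.

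**The case against.** The strongest reply is that this is one loose clause in a translated protocol. Section 7.5.4 applies once a SUSAR exists, and its working instruction is about routing: find out which vaccine was given, then submit if it is the trial vaccine. Section 9.7.6 already describes the proper order. The investigator's call comes first and without the code from 7.5.4. The either-party rule means that an unblinded sponsor cannot cancel an investigator's related call for expedited reporting. Safety is a secondary objective with no success criterion, the protocol's endpoint is the incidence of SAEs rather than related SAEs, and every SAE is listed, so reclassification hides nothing.

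Most of this stands, and it defeats three stronger readings that a reader might infer:

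- *The analysed relatedness is decided with the allocation known.* No section says so, and the only named assessor of AE causality does not receive the code under 7.5.4.
- *The suspension rule turns on an unblinded sponsor judgment.* The Grade 4 limb does not depend on SUSAR status, and the investigators prevail in a disagreement.
- *The non-interference statement in 7.5.4 is false.* It would be false only if the post-unblinding call entered the analysed data, which is not shown.

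The reply does not remove the clause itself. Helping to judge correlation is written as a purpose of unblinding. The either-party rule also works in one direction only: an unblinded sponsor cannot cancel a related call for reporting but can add one. The non-interference statement is an assertion, with no lock, timestamp or designated variable behind it.

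**Conclusion.** The point holds in a limited form. As written, 7.5.4 allows the sponsor's causality judgment on a suspected SUSAR to be made with the allocation known. This conflicts with the SUSAR definition and with 9.7.6. Whether that judgment could enter the related-SAE or related-AESI tables is left open, so the assurance in 7.5.4 is unsecured rather than untrue.

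The effect is small. Only suspected SUSARs are opened this way; expected SAEs, SAEs judged unrelated and AESIs that are not SUSARs are untouched. A single event moves a rate by 0.09 or 0.18 points, taking the planned arm sizes as denominators. The immunogenicity conclusions are not affected. The change is still worth making, because related SAEs are likely to be few, each will be read individually, and the bias can be avoided at almost no cost.

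**What to change.** - **Protocol 7.5.4:** remove the clause that makes judging correlation a purpose of unblinding. Require the investigator's and the sponsor's causality and expectedness to be recorded and locked before the code is requested. Limit the code to deciding on and routing the expedited report. Keep any later change of opinion as a separate dated entry.
- **SAP 6.1.2, 6.9.2 and 6.9.3:** state that related SAEs and AESIs use the investigator's pre-unblinding assessment.
- **Protocol 7.5.4, 7.8 and 9.7.6:** reconcile them on whether SUSAR status for the suspension criterion is set before or after the code is opened. What the suspension rule should be is not judged here.

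The cost is a few sentences across the two documents and a timestamp check in the safety database. No extra assessment is needed, since 9.7.6 already has the investigator and the sponsor each judge causality, and the sponsor judge expectedness, when an SAE is reported; only the investigator's view on expectedness would be a new entry.
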